11.1 Statistical methods include

Through deep learning method, a 16-layer convolutional neural network structure was built, which was used to extract the features of embryo images in different periods, and then the neural network model was used for statistical analysis. SPSS16.0 software was used for statistical analysis. Through the clinical results of single embryo transfer, the data were statistically analyzed with the embryo implantation rate, abortion rate and baby carrying home rate as indicators. The pregnancy rate of single embryo transfer cycle was compared with that of conventional morphology. According to the results, adjust the optimal parameter range in time to improve the accuracy and effectiveness of the prediction. To obey the normal distribution of measurement data using mean \pm standard deviation ($\bar{x} \pm s$) was described, using samples t test, inspection rate comparing with x^2 . $P < 0.05$ was considered statistically significant.

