Clinical Research Protocol: Application of deep learning automation based on
Time-lapse imaging to jointly assess embryo development to improve
pregnancy outcome of single blastocyst transfer

Subject source: the Affiliated Drum Tower Hospital of Nanjing University Medical School

Responsible person: [name]

Department: Reproductive Medicine Department

Contact person: [name]

Contact number: [name]

The research start time: December 30, 2022-June 15, 2024

Version number: AI-2021-01

The date of the document: July 01, 2021

Summary of the case

Project Name	A clinical study based on Time-lapse imaging application of deep learning automated joint evaluation of embryo development to improve the outcome of single blastocyst transplantation pregnancy
Purpose of the study	Based on Time-lapse imaging application of deep learning, this project explores the automatic evaluation model of different developmental stages of embryos, and establishes an automated joint evaluation system for the whole process of embryonic development. In addition, the patients with single blastocyst transplantation are prospectively collected, and the pregnancy outcome of the patients is followed up by TLI+AI evaluation and morphological evaluation, and the pregnancy outcome of the two groups is compared. The project aims to explore key features that play a role in the evaluation of AI embryos to provide a theoretical basis for further screening of high-quality embryos, thereby increasing the implantation rate of single embryo transfer patients, reducing multiple pregnancies and ensuring the safety of mothers and children.
Study Design	This study is an observational prospective study after a retrospective analysis. It is a single-center study without randomization or blindness. In the early stage, 1000 patients are collected from three periods of embryo culture through Time-lapse to establish an automated joint evaluation system for the whole process of embryo development. At the later stage, the patients are divided into two groups: TLI+AI assessment group and morphological assessment group. 100 patients with 5D single blastocyst transplantation are carried out to follow up the pregnancy outcome.

Total number of cases	1000 (retrospective study)+100 (prospective study)

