Case selection	
Criteria for inclusion
 
1) < 40 years of age; 2) Routine IVF cycle; 3) Period number ≤ 2; 4) The number of eggs harvested was 5-15. 5) follicle stimulating hormone (FSH) ≤ 12 IU/L on the third day of menstruation; 6) Patients with more than 3 high-quality embryos per Day 3 and feasible single blastocyst transplantation per Day 5; 7) Patient factors affecting embryo implantation such as endometrial factors.

	
Exclusion criteria
 
1) Preimplantation Genetic Testing (PGT) is needed for male infertility, ovulation cycle and chromosome abnormality.
 
2) Pictures of unformed or non-available blastocysts;
 
3) Incomplete or unclear images were collected during prokaryotic, mitotic and blastocyst phases, which affected the AI evaluation.

Treatment plan	Through conventional ovulation induction and time-lapse culture, the embryo development was observed dynamically, pictures were collected to establish an automated joint evaluation system for the whole process of embryo development, and the embryos were selected for daily 5 single blastocyst transplantation.
Evaluation of curative effect	
Efficacy evaluation indicators (primary efficacy indicators and secondary efficacy indicators)
 
Precision rate, embryo planting rate

	
Safety evaluation index
 
The harmonic mean of accuracy rate and recall rate, abortion rate

Method of statistics	
(1) Statistical analysis of the evaluation system with accuracy and recall rate;
 
(2) χ^2 test was used to compare the rates among control groups, and $p < 0.05$ was considered statistically significant.

Duration of study	December 30, 2022-June 15, 2024

Directory

1. Research background.....	1
2. Research objectives	5
3. Research design types, principles and test procedures	6
4. Case selection.....	8
5. Research methods and technical routes.....	9
6. Observation items and testing time	9
7. Evaluation criteria for curative effect.....	10
8. Observation of adverse events.....	11
9. Quality control and quality assurance of the research	11
10. Data security inspection	11
11.Statistical processing	11
12. Ethics of clinical research.....	12
13. Collection and storage of samples/specimens	12
14. References	12

List of acronyms

English abbreviation	Full English name	Full Chinese name
Assisted Reproductive Technology	ART	Assisted reproductive technology
Single embryo transfer	SET	Single embryo transfer

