3.1 Research design

This study is an observational prospective study. It is a single-center study without randomization or blind grouping. In order to establish an automated joint evaluation system for the whole process of embryo development, it is necessary to collect images of 1000 patients in the prokaryotic, mitotic and blastocyst stages of single blastocyst transplantation in IVF cycles. According to the TLI+AI assessment and morphological assessment, at least 100 cases are required for fresh cycle 5 a Day single blastocyst transplantation. At present, the pregnancy rate of single blastocyst transplantation is basically maintained at 60%. Through this study, the pregnancy rate is expected to be increased to 80%. The test standard α is 0.05.

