5.6 Study relevant imaging tests

None

6. Observation items and testing time

- 1) The morphological parameters required by the embryos were observed from Day 1-5 during embryo culture;
- 2) Images of prokaryotic stage, cleavage stage and blastocyst stage were collected for the establishment of automated embryo evaluation models at different developmental stages;
- 3) Routine luteal support after embryo transfer, positive blood HCG detected 14 days after transplantation, and pulsation of gestational sac and original cardiac tube detected by B-ultrasound at 4-6 weeks were considered as clinical pregnancy until fetal delivery.

7. Evaluation criteria for curative effect

In this study, deep learning method was used to evaluate the blastocyst quality based on neural network model and manual evaluation of blastocyst quality

In order to improve the accuracy and effectiveness of prediction, the optimal parameter range is adjusted timely according to the results.

The validity evaluation index in the study is the accuracy rate, which represents how many of the predicted positive samples are really positive samples. There are two possible predictions, one is to predict the positive class as positive class (TP), the other is to predict the negative class as positive class (FP), the accuracy rate is $P=TP/(TP+FP)$, the value is not less than 0.9. The safety evaluation index is the harmonic average of accuracy rate and recall rate $F=2*P*R/(R+P)$, that is, positive samples are not expected to be identified as negative samples, or negative samples are identified as positive samples, and the value is not less than 0.9.

In the pregnancy outcome, the clinical results of single embryo transfer were counted, and the data were statistically analyzed by the rate of embryo implantation, the rate of carrying babies home and the abortion rate of safety indicators. The pregnancy rate of single embryo transfer cycle was compared with that of conventional morphology. According to the results, adjust the optimal parameter range in time to improve the accuracy and effectiveness of the prediction.

8. Observation of adverse events

None

9. Quality control and quality assurance of the research (Determine whether this part is needed according to the specific situation of the project)

Embryo culture and transfer within the laboratory are performed in accordance with the standard SOP procedure, and the patient is given full informed consent to improve the subject's compliance.

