11.2 Sample size calculation process

At present, the pregnancy rate of single blastocyst transplantation is basically maintained at 60%. Through this study, the pregnancy rate is expected to be increased to 80%. The test standard α is 0.05.

12. Ethics of clinical research

Clinical research will follow the relevant regulations such as the Declaration of Helsinki of the World Medical Congress. Clinical studies are conducted only after the protocol is approved by the Ethics Committee prior to the start of the study. Before each subject is enrolled in this study, the investigator is responsible to give a complete and comprehensive introduction of the purpose, procedure and possible risks of this study to the subject or his/her agent, and sign a written informed consent. Subjects should be informed that they have the right to withdraw from this study at any time, and informed consent should be kept as a clinical study document for future reference. Subjects' privacy and data confidentiality will be protected during the study.

13. Collection and storage of samples/specimens

In this study, images of embryos were collected every 15 minutes by time-lapse system, and all the images were stored in the computer hard drive. It is stored in the hard disk of the computer of the center. It is backed up regularly every year and kept completely indefinitely.

14. References

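### The protocol does not settle its deciding endpoint: it is sized on pregnancy rate, its efficacy list names precision and implantation, and several rates are each tested at 0.05 with no hierarchy.

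*Protocol*

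**What the plan says.** **Sizing (Protocol 3.1 and 11.2).** The only planning assumption concerns pregnancy: "the pregnancy rate of single blastocyst transplantation is basically maintained at 60" per cent, and "the pregnancy rate is expected to be increased to 80" per cent. The section closes with "The test standard α is 0.05".

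**Objective (2.1).** The clinical aim is stated as a better implantation rate in single-transfer patients. Pregnancy rate is not named.

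**Synopsis, evaluation of curative effect.** One heading covers primary and secondary efficacy indicators together. Its whole content is "Precision rate, embryo planting rate". Pregnancy rate is absent and neither item is marked as primary. The safety row holds the F measure and the abortion rate.

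**Study endpoint (3.4).** This names no outcome, only the completion of data collection and analysis in 100 patients.

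**Research steps (3.2, part 3).** Follow-up covers implantation, abortion and take-home-baby rates, again without pregnancy rate.

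**Section 7.** Precision is the validity index, judged against 0.9. The clinical part then uses "the rate of embryo implantation, the rate of carrying babies home and the abortion rate of safety indicators", and adds a comparison of pregnancy rate with conventional morphology.

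**Section 11.1.** The clinical data are analysed "with the embryo implantation rate, abortion rate and baby carrying home rate as indicators". Pregnancy rate is again compared as well. Rates are tested by chi-square, and P < 0.05 is the only criterion.

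**The concern.** A sample size belongs to one endpoint. Here the rate used for sizing is not on the efficacy list, and the list itself does not separate primary from secondary. A reader who asks which result decides whether AI-assisted selection improved the outcome gets a different answer from each section: pregnancy in 3.1 and 11.2, implantation in 2.1, precision or implantation in the synopsis, and any of four rates in 7 and 11.1.

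Two things are at stake. First, the choice of the headline result is left open until the data are in, and the chance that some rate crosses 0.05 by luck is above the nominal level. Second, the 60% and 80% cannot be tied with certainty to whichever rate is finally reported.

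A multiplicity rule could sit in a statistical analysis plan that is not shown. The name of the primary endpoint and its match to the sizing belong in the protocol, and the protocol has already fixed them inconsistently.

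**Working it through.** **1. The plan's own figure.** The stated size is "1000 (retrospective study)+100 (prospective study"), and 3.1 says "at least 100 cases are required for fresh cycle 5 a Day single blastocyst transplantation". Power, sidedness and allocation are not given. For 60% against 80%, two-sided 0.05 and 80% power:

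n per group = [1.96 × √(2 × 0.7 × 0.3) + 0.8416 × √(0.6 × 0.4 + 0.8 × 0.2)]² / 0.2² = (1.270 + 0.532)² / 0.04 ≈ 81.2, so 82.

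With 50 per group the two-sided power is 59.0%; with 100 per group it is 87.6%. The 100 can be neither confirmed nor refuted from what is stated. That is a separate matter. It matters here only because the calculation is tied to pregnancy rate and to no other outcome.

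**2. Which outcome each section points to.**

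| Place | Outcome named | Marked as primary? |
|---|---|---|
| 2.1 | implantation | no |
| 3.1, 11.2 | pregnancy | no, but it carries the sizing |
| 3.4 | none | no |
| Synopsis, efficacy | precision, implantation | primary and secondary merged |
| 3.2 part 3 | implantation, abortion, take-home baby | no |
| 7, 11.1 | implantation, abortion, take-home baby, and pregnancy | no |

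No section resolves the others.

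**3. Size of the multiplicity.** If the tests were independent, the chance of at least one false positive would be 1 − 0.95³ = 14.3% for three tests and 1 − 0.95⁴ = 18.5% for four. The outcomes are nested, so these figures are too high. I simulated null trials (400,000 per scenario) with implantation, then clinical pregnancy among those implanted, then loss among pregnancies, and take-home baby as pregnancies not lost. Each rate was tested by uncorrected chi-square at two-sided 0.05.

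Inputs:
- Clinical pregnancy 60%: the protocol's pregnancy rate, read here as pregnancy with heartbeat.
- Implantation 60-70%: assumed. At 60% it is identical to clinical pregnancy.
- Loss 10-20% of pregnancies: assumed.
- 50 per group: assumed, because no allocation is stated.

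| Counted as a false positive | Chance under no difference |
|---|---|
| Pregnancy alone, two-sided | about 5% |
| Pregnancy alone, favouring AI | about 2.6% |
| Any of implantation, pregnancy, take-home baby, two-sided | about 8-11% |
| The same three, favouring AI only | about 4-5.5% |
| All four including abortion, two-sided | about 11-14% |

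The results are almost the same with 100 per group, so the assumed split hardly affects them.

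**4. Where the inflation comes from.** Implantation and pregnancy together give about 5.2% if they coincide and about 7.2% if implantation is 65%. The rest of the efficacy figure comes from adding take-home baby.

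**The case against.** **The mismatch may be largely one of words.** Every prospective patient receives one blastocyst, so implantation per embryo is also per patient. If implantation is judged on ultrasound, it nearly equals clinical pregnancy as section 6 describes it. A reader might infer that the 60% and 80% do not apply to implantation at all. The protocol does not show that. Equally, it never defines implantation, so the two cannot be presumed equal. This part of the objection stands as a limit on the point and does not answer it.

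**The inflation depends on what is counted.** A reader might take 11-14% as the rate of false success claims. That overstates it, because the count includes abortion, which the synopsis and section 7 label as safety, and results against AI. The fair figures are 8-11% two-sided for the three efficacy rates, and 4-5.5% in favour of AI.

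**No success rule is written.** A reader might infer that any one of four significant tests would be declared a success. The P < 0.05 sentence is a general threshold, and the protocol does not say this. What can be said is that nothing in it identifies the test that decides.

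**Precision is already mostly separate.** Sections 3.2 and 7, and the synopsis row on statistics, treat precision and F as model metrics. Only the synopsis rows on efficacy and safety mix them with patient outcomes. This stands.

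**The study is observational and not randomised.** The null calculation assumes comparable groups, which this design does not secure. The figures therefore show the effect of multiple testing alone and are not the study's total error.

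**Conclusion.** The point holds as an internal contradiction. The sizing endpoint, the stated objective and the efficacy list do not agree, and four clinical rates are compared under one 0.05 threshold with no order among them.

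Under the assumptions listed, the consequence is moderate: a false positive on at least one efficacy rate rises from about 5% to about 8-11% two-sided, or from about 2.6% to about 4-5.5% in favour of AI. The lower ends apply if implantation and clinical pregnancy are the same event. The implantation and loss rates are assumptions, and only the 60% comes from the protocol. The naming problem does not depend on any of these figures.

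**What to change.** - Name one primary endpoint that matches the sizing, and use the same term in the synopsis and in sections 7, 11.1 and 11.2. Test only that endpoint at 0.05.
- Clinical pregnancy per patient, as described in section 6, is the natural choice: it is already defined and is closest to the rate used for sizing. If the sponsor prefers implantation, define it and restate the 60% and 80% for that definition.
- Report the remaining clinical rates as secondary, with differences and 95% confidence intervals, and make no success claim from their p-values.
- In the synopsis, list precision and F under the model-building stage only.

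The cost is wording: no new data, visits or change in the sizing alpha. The sponsor gives up the option of claiming success on a secondary outcome alone. The alternative of keeping three deciding tests with a Bonferroni split costs more. At 0.05/3 = 0.0167, 60% against 80% needs 109 per group for 80% power instead of 82.

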3.2 Research steps

(1) Establish an AI-time lapse automated combined embryo evaluation system to improve the accuracy of embryo evaluation

1) According to the entry and expulsion criteria, 1000 patients were enrolled and Time-lapse closed-loop culture embryo images of prokaryotic phase, mitotic phase and blastocyst phase were collected.

2) To establish the inclusion criteria for training samples, screen and sort out embryo picture samples;

3) Five embryologists annotated the image samples to generate training sample sets and test sample sets;

4) Convolutional neural network based on deep learning was used to build the prokaryotic detection network, the splintering period counting network, the splintering period segmentation network and the blastocyst region segmentation network, and train the detection models in each period respectively;

5) The convolutional neural network classification model is built to classify the embryo quality, and the AI-time lapse automatic joint embryo evaluation system is established by using the five-fold crossover method to train and verify the model.

(2) Debug the generalization ability of the model and improve the evaluation function of embryonic development

1) Test the generalization ability of the AI evaluation model by using embryo picture data, and visualize the features dependent on the model classification.

2) Comparative analysis of AI evaluation and manual evaluation, optimization of model with transfer learning method, and improvement of model accuracy.

(3) To verify the automated combined embryo assessment system to improve the pregnancy outcome of single blastocyst transplantation

1) The enrolled subjects undergoing monoblastocyst transplantation were screened, and informed consent was signed with the patients;

2) Routine ovulation, fertilization and embryo culture in time lapse system for dynamic observation;

3) The optimal blastocysts were selected by AI-time lapse system for combined evaluation and manual evaluation, and 100 cases with fresh cycle of 5 blastocysts per Day were prospective performed.

4) The pregnancy outcomes of the two groups, including the implantation rate, abortion rate and the rate of carrying babies home, were followed up for statistical analysis.

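### Sections 7 and 11.1 direct that the parameter range be adjusted according to the results, straight after the pregnancy-rate comparison, without saying whether this is during or after the prospective transfers that are meant to verify the system

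*Protocol*

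**What the plan says.** Section 3.2 of the Protocol sets out three steps. Step (1) builds the AI system from the images of 1000 patients. Step (2) tests and tunes it, including "optimization of model with transfer learning method, and improvement of model accuracy". Step (3) is the prospective stage, and its stated purpose is "To verify the automated combined embryo assessment system to improve the pregnancy outcome of single blastocyst transplantation". In that stage the system takes part in choosing the embryo: "The optimal blastocysts were selected by AI-time lapse system for combined evaluation and manual evaluation". The 100 prospective patients are then followed for pregnancy outcome, and rates are compared by chi-square test at p < 0.05.

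Three sentences direct an adjustment of the parameter range:

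- Section 7, second paragraph, before the accuracy definitions: "the optimal parameter range is adjusted timely according to the results".
- Section 7, last paragraph, on pregnancy outcome: "The pregnancy rate of single embryo transfer cycle was compared with that of conventional morphology. According to the results, adjust the optimal parameter range", with the same ending as in section 11.1.
- Section 11.1, among the statistical methods and again just after the comparison with conventional morphology: "According to the results, adjust the optimal parameter range in time to improve the accuracy and effectiveness of the prediction".

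None of the three gives a time in relation to the prospective transfers. The available text nowhere fixes the model, its weights or its cut-offs before the first of them.

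**The concern.** A stage that verifies a system needs one defined system to verify. Here the protocol tells staff to change the parameters according to results, and in two of the three places the nearest results are the pregnancy outcomes of the stage that does the verifying.

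If staff follow the instruction while transfers are still under way, later patients in the AI group have their blastocyst chosen by a different version from earlier patients, and that version has been tuned on the earlier patients' outcomes. The AI group's pregnancy rate is then an average over versions. A favourable chi-square result could not be assigned to any version that could be named and used afterwards, and the outcomes used for tuning would not be independent evidence for the tuned version.

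**Working it through.** The point rests on wording, and the plan has no figure of its own to reproduce. The check is to set the sentences against the study sequence and then ask whether adjustment during the transfers would be possible.

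**1. Which results each sentence refers to.**

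- *Section 7, second paragraph.* It stands between the sentence on neural-network and manual evaluation of blastocyst quality and the definitions of P = TP/(TP+FP) and F = 2PR/(R+P), each required to be at least 0.9. Its subject is model performance. This matches step (2), so it most naturally concerns development.
- *Section 7, last paragraph, and section 11.1.* The sentence immediately before is the pregnancy-rate comparison, so the results meant include the prospective outcomes. The two instructions are word for word the same, which makes them one instruction given twice.

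**2. What each timing would imply.**

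| Timing of adjustment | System used for the AI group | What the chi-square comparison shows |
|---|---|---|
| During the prospective transfers | Several versions, later ones tuned on earlier outcomes | No single system is verified |
| Only after the comparison | One version | Valid for the version tested; the adjusted version needs its own data |

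Only the first row harms the verification.

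**3. Is the first row possible within the study's own times?** The study period is "December 30, 2022-June 15, 2024": 365 days to December 30, 2023, plus 168 days to June 15, 2024, which is 533 days. Section 6 defines clinical pregnancy by "positive blood HCG detected 14 days after transplantation, and pulsation of gestational sac and original cardiac tube detected by B-ultrasound at 4-6 weeks". Counting the ultrasound weeks from transfer (an assumption), a result is known after L = 14 days (HCG) to at most L = 42 days (ultrasound).

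The length of the transfer period, W, is not given. Assume 100 transfers evenly spaced from day 0 to day W, so that transfer i takes place on day i × W/99, with i = 0 to 99. Its result is known by the day of the last transfer if i ≤ 99 × (W − L)/W. For W = 90 and L = 42 the limit is 99 × 48/90 = 52.8, so transfers 0 to 52 qualify, which is 53. The longest W that leaves 42 days for the last ultrasound is 533 − 42 = 491, if transfers could start on day 0.

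| W (assumed, days) | Known by last transfer, L = 42 | Known by last transfer, L = 14 |
|---|---|---|
| 90 | 53 of 100 | 84 of 100 |
| 180 | 76 of 100 | 92 of 100 |
| 365 | 88 of 100 | 96 of 100 |
| 491 | 91 of 100 | 97 of 100 |

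The size of the AI group is not stated. With 50 transfers and L = 42, the counts are 27, 38, 44 and 45. Outcomes would therefore be at hand in time to act on. The counts show only that adjustment during the transfers is practicable. They do not show that it is intended.

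**The case against.** The strongest case against is that the protocol already implies the harmless order. Section 3.2 puts building and optimisation before verification, and the synopsis separates an early stage that establishes the system from a later stage that follows pregnancy outcomes. In sections 7 and 11.1 the text compares first and adjusts second. No part of the available text describes an interim look or retraining on prospective outcomes. The document also reads as a translation, so the phrase about timing is thin evidence of real-time updating. It speaks of a parameter range without naming the AI model, although the stated aim of better prediction makes the model the natural object.

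Much of this stands. Adjustment after the study is at least as natural a reading as adjustment during it. A reader might infer that the protocol plans to retune the system mid-study; the documents do not say so. A reader might also infer that on any reading one cannot tell which version the result belongs to. That is wrong: if adjustment comes only afterwards, the result belongs to the version used for the transfers. The need for new data on a later version applies to any system refined after a study and is no error here.

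It may also be said that a model lock could stand in a statistical analysis plan that is not shown. The absence of a lock alone would be no finding. The point rests on what the protocol states: an instruction to adjust on results, placed after the verification outcomes, with no time limit. A lock elsewhere would still have to be reconciled with that instruction. The order of steps (1) to (3) does not supply the limit either, because the instruction is repeated outside that sequence, within the outcome evaluation and the statistical methods.

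**Conclusion.** The point holds in a limited form. One instruction, given in section 7 (last paragraph) and in section 11.1, permits tuning on the outcomes that step (3) uses to verify the system, because its timing is not stated. The harm is conditional on the instruction being followed during the prospective transfers. The second-paragraph sentence in section 7 is not counted as further evidence, since it most naturally belongs to model development.

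No bias, loss of power or change in error rate is quantified or claimed, because nothing in the protocol says how often or how far the range would be adjusted. The feasibility counts depend on even spacing and assumed transfer periods. The issue should be fixed because it is cheap to settle and protects the study's ability to say which system it verified.

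**What to change.** 1. In section 7 (last paragraph) and section 11.1, replace the adjustment sentence with: *After the analysis of the prospective patients is complete, the parameter range may be adjusted; any adjusted system is a new version and needs validation on new data.* Rewording is better than deletion, because section 2.2 makes the search for new indexes and methods a secondary purpose.
2. In the second paragraph of section 7, limit the adjustment to model development, that is, to steps (1) and (2) of section 3.2.
3. In step (3) of section 3.2, add: *The model, its weights and its cut-offs are locked and version-numbered before the first prospective transfer and stay unchanged until the prospective analysis is complete.*

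This changes protocol wording only and adds no patients or procedures. The downside is that improvements found during the study wait for the next version, which will need its own validation data.
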